3.2 BACKGROUND

[REDACTED]

[REDACTED]

[REDACTED]

3.3 RISK/BENEFIT ASSESSMENT

3.3.1 KNOWN POTENTIAL RISKS

Since this is the first-in-human (FIH) clinical study with INV-102 topical ocular solution, the risk profile for the compound in humans has not been determined.

[REDACTED]

3.3.2 KNOWN POTENTIAL BENEFITS

This is the first study of INV-102 topical ocular solution in humans and, therefore, benefits from its use have not been established.

[REDACTED]

3.3.3 POTENTIAL IMPACT OF THE COVID-19 PANDEMIC

In acknowledgement of hospital, local, state, or national government Coronavirus Disease 2019 (COVID-19) restrictions or other site- or subject-related factors, which may prevent investigators from conducting certain assessments or procedures according to the Schedules of Activities (SoAs), investigators may seek approval from Invirsa to modify when or if certain assessments or procedures are conducted according to the SoAs. While sites must employ all efforts to see subjects in the clinic for assessments, exceptions may be granted for alternative methods for conducting subject visits with approval by Invirsa and notification to the Institutional Review Board (IRB). In evaluating such requests, the Invirsa team will give the highest priority to the safety and welfare of the subjects. Investigators are expected to evaluate the impact to the safety of the subjects and site personnel for subjects to continue. Subjects must be willing and able to continue receiving study drug and remain compliant with the protocol. For subjects who are impacted, any procedures not conducted per the original study plan will be documented in the study records.

When approval is given for a subject to miss an in-person visit, site staff will speak directly with the subject by telephone or other medium (eg, a computer-based video communication) during each visit window to assess subject safety and overall clinical status. During this contact with the subject, the investigator or other qualified site staff should also, at a minimum, conduct the following assessments: adverse event (AE) collection and concomitant medication documentation. Other study assessments may be collected remotely as feasible. Sites may also seek approval to extend a visit window in order to conduct an onsite visit.

Data collected with alternative methods may be handled differently in the final data analyses. This will be documented in the Statistical Analysis Plan (SAP).

4 OBJECTIVES AND ENDPOINTS

Part 1 (Dose Escalation)

OBJECTIVES	ENDPOINTS	JUSTIFICATION FOR ENDPOINTS
Primary		
To characterize the safety profile of INV-102 in subjects with moderate symptomatic DED using multiple concentrations and dosing regimens	Safety endpoint: treatment-emergent adverse events (TEAEs)	Safety endpoint assessing the ocular and systemic safety of INV-102 is necessary in this FIH study
Other		

OBJECTIVES	ENDPOINTS	JUSTIFICATION FOR ENDPOINTS
Part 2 (Optional Dose Expansion)		
OBJECTIVES	ENDPOINTS	JUSTIFICATION FOR ENDPOINTS
Primary		
To evaluate the efficacy of INV-102 in subjects with moderate symptomatic DED in an expanded cohort	Efficacy endpoint using change from Baseline to Day 15 in either the eye dryness score or eye discomfort score from the [REDACTED] DED symptom VAS (the specific endpoint for Part 2 will be chosen based on results from Part 1 [Dose Escalation] Cohorts 1 to 4 [REDACTED])	An efficacy endpoint using a subject-reported outcome of DED symptoms is useful to provide preliminary information regarding the efficacy of INV-102 in the treatment of DED
Secondary		
To evaluate the efficacy of INV-102 using signs and symptoms in a combined outcome score in subjects with moderate symptomatic DED	Efficacy endpoint chosen as per primary endpoint (change from Baseline to Day 15): Eye Dryness Composite Score or Eye Discomfort Composite Score	Efficacy endpoint using 2 subject-reported outcomes (assessing DED symptoms) and 1 objective measure of DED signs (corneal fluorescein staining) is useful to provide preliminary information regarding the efficacy of INV-102 in the treatment of DED. A composite score combining symptoms (VAS individual item score) and signs (corneal fluorescein staining) will provide a more robust measure of efficacy
Other		

OBJECTIVES	ENDPOINTS	JUSTIFICATION FOR ENDPOINTS

5 STUDY DESIGN

5.1 OVERALL DESIGN

This FIH, multicenter, Phase 1/2 study has a randomized, double-masked, vehicle-controlled MAD part (Part 1) and an optional randomized, double-masked, vehicle-controlled dose-expansion part (Part 2) to evaluate INV-102 in subjects with moderate symptomatic DED. Part 1 will be a Dose Escalation phase across 4 cohorts of subjects to assess safety, tolerability, and systemic PK of INV-102, and Part 2 will be an Optional Dose Expansion phase in a fifth cohort of subjects conducted pending the outcome of Part 1, to assess efficacy of INV-102 in the treatment of moderate symptomatic DED.

Prescription eyedrops/medications for DED must be washed out and contact lens wear must be discontinued [REDACTED] and both are prohibited throughout the dosing and follow-up phases of the study. Over-the-counter eyedrops, [REDACTED] are also prohibited throughout the dosing and follow-up phases of the study.

In Part 1 (Dose Escalation) Cohorts 1 to 4, both eyes (OU) will receive study drug and data from each eye will be analyzed. In Part 2 (Optional Dose Expansion) Cohort 5, only eyes meeting DED eligibility (ie, Qualifying Eyes) will receive study drug and data only from those eyes will be analyzed. However, regardless of whether subjects receive study drug in one or both eyes, all subjects in both parts of the study will have only one eye designated as the Study Eye. The Study Eye is the eye with more severe DED based on corneal fluorescein staining. The other eye is designated as the Fellow Eye. If both eyes have the same corneal fluorescein staining score, the eye with the more severe eye dryness score from the [REDACTED] DED symptom VAS will be the Study Eye. If both eyes also have the same eye dryness score, the right eye will be the Study Eye.

In Part 1 (Dose Escalation), subjects will be enrolled in a sequential manner into 1 of 4 cohorts, where they will be randomized 2:1 to receive either INV-102 or vehicle, respectively. Enrollment of the next cohort can begin once the current cohort is fully enrolled [REDACTED]

In Part 1, subjects will instill topical ocular study drug (INV-102 or vehicle) in both eyes for 2 weeks. (**Note:** study drug will be dosed in both eyes in Part 1 regardless of whether both eyes meet the criteria as a Qualifying Eye). The formulation concentration and frequency of dosing will be determined by cohort, with Cohorts 1 to 3 receiving BID dosing (approximately every 12 hours with at least 6 hours between doses) and Cohort 4 receiving TID dosing (approximately every 8 hours with at least 6 hours between doses). Subjects who fail to take a dose of study drug within the dosing window should skip that dose and not attempt to make it up.

- Cohort 1 (0.1% INV-102 vs vehicle): 1 drop OU on Day 1, then BID OU for 13 days (Days 2-14), then 1 drop OU on Day 15
- Cohort 2 (0.25% INV-102 vs vehicle): 1 drop OU on Day 1, then BID OU for 13 days (Days 2-14), then 1 drop OU on Day 15

- Cohort 3 (0.7% INV-102 vs vehicle): 1 drop OU on Day 1, then BID OU for 13 days (Days 2-14), then 1 drop OU on Day 15
- Cohort 4 (0.7% INV-102 vs vehicle): 1 drop OU on Day 1, then TID OU for 13 days (Days 2-14), then 1 drop OU on Day 15

After Part 1 (Dose Escalation) Cohorts 1 to 4 have been completed and Cohort 4 has been fully enrolled [REDACTED] the study may advance to the optional Part 2 based on review of available [REDACTED] data [REDACTED].

In Part 2 (Optional Dose Expansion) Cohort 5, subjects will be randomized 2:1 to INV-102 or vehicle, respectively, and will instill topical ocular study drug in eligible eye(s) (ie, Qualifying Eyes) for 2 weeks either BID (1 drop on Day 1, then BID for 13 days, then 1 drop on Day 15) or TID (1 drop on Day 1, then TID for 13 days, then 1 drop on Day 15). Frequency and dose will be chosen [REDACTED] based on the results from Part 1 (Dose Escalation) Cohorts 1 to 4 (**Note:** study drug may be dosed in a single eye or in both eyes in Part 2, depending on whether each eye individually meets the criteria as a Qualifying Eye. For subjects dosing only one eye in Part 2 [ie, having only one Qualifying Eye], assessments will only be performed on the eye being dosed).

5.2 MASKING OF SUBJECTS, SITE PERSONNEL, AND STUDY PERSONNEL

Masking of individual subject study drug assignments will be maintained throughout the study for all subjects and all site and study personnel, aside from designated personnel assigned to review the data from Cohorts 1 to 4 for purposes of selecting the dose for Part 2 (Optional Dose Expansion) as defined in the Unmasked Data Review Plan, until the database is locked for the final analysis. If it is necessary for the safety and appropriate treatment of a subject, the study drug assignment can be unmasked. When possible, the medical monitor should be notified prior to the unmasking, and the reason for breaking the mask will be documented. The investigator should inform the medical monitor of the unmasking if there is no notification prior to the unmasking.

5.3 SCIENTIFIC RATIONALE FOR STUDY DESIGN

The first part of the study is designed as a dose-escalation, FIH Phase 1 study. Part 1 (Dose Escalation) will assess safety at various INV-102 dose levels and aid in the determination of the dose for Part 2 [REDACTED]. Part 2 (Optional Dose Expansion) is the optional Phase 2 portion of the study and is intended to assess both safety and gather expanded efficacy [REDACTED] for INV-102 in subjects with DED.

Both parts of the study are randomized to INV-102 or vehicle. Vehicle is useful in this Phase 1/2 study because some of the endpoints are subjective. Therefore, it is important to assess responses of subjects receiving vehicle to account for any placebo effect, in which subjects may believe their disease is improving simply because they are receiving study drug. The 2:1 (INV-102:vehicle) ratio of subject assignment was chosen so that the majority of subjects will receive INV-102.

5.4 JUSTIFICATION FOR DOSE

Topical INV-102 has been shown to be efficacious in rabbit models

Therefore, INV-102 is anticipated to be safe and effective when dosed in the concentration range from 0.1% to 0.7%, administered as 30 µL drops, BID or TID OU for 14 days. In Part 1 (Dose Escalation) of this study, the first 4 cohorts will receive study drug as follows:

- Cohort 1 (0.1% INV-102 vs vehicle): 1 drop OU on Day 1, then BID OU for 13 days (Days 2-14), then 1 drop OU on Day 15
- Cohort 2 (0.25% INV-102 vs vehicle): 1 drop OU on Day 1, then BID OU for 13 days (Days 2-14), then 1 drop OU on Day 15
- Cohort 3 (0.7% INV-102 vs vehicle): 1 drop OU on Day 1, then BID OU for 13 days (Days 2-14), then 1 drop OU on Day 15
- Cohort 4 (0.7% INV-102 vs vehicle): 1 drop OU on Day 1, then TID OU for 13 days (Days 2-14), then 1 drop OU on Day 15

The dose and frequency for Part 2 (Optional Dose Expansion) will be determined by the results of the 4 cohorts in Part 1. Subjects will instill study drug in eligible eye(s) only [ie, Qualifying Eye(s)] using the regimen of either BID (1 drop on Day 1, then BID for 13 days (Days 2-14), then 1 drop on Day 15) or TID (1 drop on Day 1, then TID for 13 days (Days 2-14), then 1 drop on Day 15).

5.5 END OF STUDY DEFINITION

A subject is considered to have completed the study if he or she has completed the dosing and follow-up phases of the study, including the last visit or the last scheduled procedure shown in the SoA ([Section 1.3](#)).

The end of the study is defined as completion of the last visit or procedure shown in the SoA in the trial globally.

6 STUDY POPULATION

6.1 INCLUSION CRITERIA

In order to be eligible to participate in this study, an individual must meet all of the following criteria:

1. Healthy male or female subject ≥ 18 years of age
2. Presence of moderate DED in at least one eye [REDACTED] as defined by the following criteria (for an eye to qualify, all criteria must be present in the same eye):
 - [REDACTED]
 - [REDACTED]
 - [REDACTED]
3. Ability to comply with all protocol-mandated procedures and to attend all scheduled office visits
4. Able to self-administer study drug or to have the study drug administered by a caregiver throughout the study period

6.2 EXCLUSION CRITERIA

An individual who meets any of the following criteria will be excluded from participation in this study:

1. Best-corrected visual acuity [REDACTED] as assessed using an Early Treatment Diabetic Retinopathy Study (ETDRS) chart
2. Intraocular pressure [REDACTED]
3. Presently using prescription eyedrops, [REDACTED]
4. Use of OTC eyedrops [REDACTED]
5. [REDACTED]
6. [REDACTED]
7. External eye disease [REDACTED]
8. [REDACTED]

- [REDACTED]

6.3 SCREEN FAILURES

Screen failures are defined as participants who consent to participate in the clinical trial but are not subsequently randomly assigned to the study intervention or entered in the study. A minimal set of screen failure information is required to ensure transparent reporting of screen failure participants, to meet the Consolidated Standards of Reporting Trials (CONSORT) publishing requirements, and to respond to queries from regulatory authorities. Minimal information includes [REDACTED]

[REDACTED]

[REDACTED]

6.4 STRATEGIES FOR RECRUITMENT AND RETENTION

[REDACTED]

7 STUDY INTERVENTION

7.1 STUDY INTERVENTIONS ADMINISTRATION

7.1.1 STUDY INTERVENTION DESCRIPTION

INV-102 Ophthalmic Solution is a topical eyedrop containing the active ingredient INV-102. INV-102 is

Vehicle Ophthalmic Solution is identical to the formulation of INV-102 Ophthalmic Solution but does not contain the active ingredient.

7.1.2 DOSING AND ADMINISTRATION

INV-102 is provided in concentrations of 0.1%, 0.25%, and 0.7%.

In Part 1 (Dose Escalation), subjects will be enrolled in a sequential manner into 1 of 4 cohorts as shown below, where they will be randomized 2:1 to receive either INV-102 or vehicle, respectively. Enrollment of the next cohort can begin once the current cohort is fully enrolled

. Subjects will instill topical ocular study drug (INV-102 or vehicle) in both eyes for 2 weeks. Study drug will be dosed in both eyes in Part 1 regardless of whether they meet the criteria as a Qualifying Eye. The formulation concentration and frequency of dosing will be determined by cohort, with Cohorts 1 to 3 receiving BID dosing (approximately every 12 hours with at least 6 hours between doses) and Cohort 4 receiving TID dosing (approximately every 8 hours with at least 6 hours between doses). Subjects who fail to take a dose of study drug within the dosing window should skip that dose and not attempt to make it up.

- Cohort 1 (0.1% INV-102 vs vehicle): 1 drop OU on Day 1, then BID OU for 13 days (Days 2-14), then 1 drop OU on Day 15
- Cohort 2 (0.25% INV-102 vs vehicle): 1 drop OU on Day 1, then BID OU for 13 days (Days 2-14), then 1 drop OU on Day 15
- Cohort 3 (0.7% INV-102 vs vehicle): 1 drop OU on Day 1, then BID OU for 13 days (Days 2-14), then 1 drop OU on Day 15
- Cohort 4 (0.7% INV-102 vs vehicle): 1 drop OU on Day 1, then TID OU for 13 days (Days 2-14), then 1 drop OU on Day 15

In Part 2 (Optional Dose Expansion), subjects in Cohort 5 will be randomized 2:1 to INV-102 or vehicle, respectively, and will instill topical ocular study drug in eligible eye(s) (ie, Qualifying Eyes) for 2 weeks either BID (1 drop on Day 1, then BID for 13 days, then 1 drop on Day 15) or TID (1 drop on Day 1, then TID for 13 days, then 1 drop on Day 15). Frequency and dose chosen based on the results from Part 1 (Dose Escalation) Cohorts 1 to 4. Study drug may be dosed in a single eye or in both eyes in Part 2 depending on whether each eye individually meets the criteria as a Qualifying Eye.

7.2 PREPARATION/HANDLING/STORAGE/ACCOUNTABILITY

7.2.1 ACQUISITION AND ACCOUNTABILITY

The investigator or designee (eg, study coordinator or pharmacist) will maintain a full accountability record for the study drug and will be responsible for recording the receipt, dispensing, and return of all supplies of the study drug using the inventories supplied for the study. The investigator or designee will account for all study drug. The monitor will review dispensing and study drug accountability records during study visits, or remotely, if applicable, and at the completion of the study and note any discrepancies.

When the study is completed or is terminated by Invirsa, all study material, including used and unused study drug, will be returned to Invirsa (or its designee) or destroyed under the specific direction of same. All study drug accounting procedures must be completed before the study is considered completed. A final study drug disposition will be completed by the study coordinator.

7.2.2 FORMULATION, APPEARANCE, PACKAGING, AND LABELING

INV-102 Ophthalmic Solution is [REDACTED]

Vehicle Ophthalmic Solution is identical to the formulation of INV-102 Ophthalmic Solution but does not contain the active ingredient.

Both study drug and vehicle are provided in a multi-use eyedrop sterile container closure system [REDACTED]

[REDACTED] The bottle will be labeled with an investigational label showing the study protocol number and other relevant information, including a statement "Caution – New Drug – Limited by Federal (US) Law to Investigational Use".

7.2.3 PRODUCT STORAGE

Prior to dispensing, all study drug must be stored in a secure locked location with access limited to authorized persons who may dispense investigational materials. [REDACTED]

7.3 RANDOMIZATION

Prior to initiation of study drug dosing, 2:1 randomization (INV-102:vehicle) will occur by site personnel [REDACTED] once it is confirmed that the subject meets the study entry criteria. [REDACTED] provide the subject identification number listed on all study documents and used to manage the randomization and study drug assignment based on a central randomization

scheme [REDACTED] Study drug will be labeled with medication kit (bottle) numbers, and [REDACTED] provide each site with the specific medication kit number for each randomized subject at the time of randomization. Sites will dispense study drug according to [REDACTED] instructions and will [REDACTED] confirmation notifications for each transaction. All notifications are to be maintained with the study source documents.

7.4 STUDY INTERVENTION COMPLIANCE

Dosing compliance will be assessed by [REDACTED]

[REDACTED]

[REDACTED]

Noncompliance at Day 8 will result in re-education of the subject, and noncompliance at either Day 8 or Day 15 will be recorded as a protocol deviation.

7.5 CONCOMITANT THERAPY

All medications taken within 30 days prior to the start of study drug and during the trial (through the Follow-Up Visit) should be recorded on the appropriate electronic case report form (eCRF).

[REDACTED]

[REDACTED]

[REDACTED]

[REDACTED]

[REDACTED]

[REDACTED]

[REDACTED]

[REDACTED]

[REDACTED]

[REDACTED]

7.5.1 RESCUE MEDICINE

Not applicable.

8 STUDY INTERVENTION DISCONTINUATION AND SUBJECT DISCONTINUATION/WITHDRAWAL

8.1 DISCONTINUATION OF STUDY INTERVENTION

Study drug may be discontinued for the following reasons:

- **Adverse events:** Adverse events include clinically significant laboratory abnormalities and intercurrent diseases reported by the subject or observed by the investigator or designee with documentation on the eCRF
- **Death:** If a subject dies, the AE that caused the death should be documented on the eCRF and be noted as serious and fatal
- **Investigator decision:** A subject may be discontinued for reasons other than those bulleted previously if the investigator thinks it is not in the best interest of the subject to continue
- **Other:** Any other reason for subject discontinuation should be noted on the eCRF

The reason for premature study drug discontinuation should be recorded on the eCRF.

8.2 SUBJECT WITHDRAWAL FROM THE STUDY

Subjects are free to withdraw from participation in the study at any time, for any reason, and without prejudice. An investigator may withdraw a subject from the study for the following reasons:

- Pregnancy
- Noncompliance with study drug
- Lost to follow-up
- Any clinical AE or other medical condition or situation such that, in the opinion of the investigator, continued participation in the study would not be in the best interest of the subject
- Safety concern by the investigator or Sponsor

[REDACTED]

The reason for subject withdrawal from the study should be recorded on the eCRF. [REDACTED]

[REDACTED]

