10.2 POPULATIONS FOR ANALYSES

Three analysis populations will be defined and used in the statistical analyses: (1) a safety population, (2) a modified intent-to-treat (mITT) population, and (3) a per protocol (PP) population. Separate analysis populations will be defined in each part of the study.

Safety population: The safety population will include all randomized subjects who received at least 1 drop of study drug. The safety population will be used to summarize safety variables, using the study drug they actually received.

Modified intent-to-treat population: The mITT population will include all randomized subjects who received at least 1 drop of study drug in the Study Eye and completed at least 1 scheduled post-dosing assessment in the Study Eye. The mITT population will be used to analyze all efficacy endpoints, with subjects included in their randomized study drug regardless of the study drug they actually received. The Study Eye is defined as the eye with more severe disease based on corneal fluorescein staining. The other eye is designated as the Fellow Eye. If both eyes have the same corneal fluorescein staining score, the eye with the more severe eye dryness score from the [REDACTED] DED symptom VAS will be the Study Eye. If both eyes have the same eye dryness score, the right eye will be the Study Eye.

Per protocol population: The PP population includes all subjects in the mITT population who have study drug compliance of $\geq 80\%$ as defined by [REDACTED] and have no major protocol deviations considered to have significant impact on study drug outcome. The PP population will be used to analyze selected efficacy endpoints.

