10.3.2 ANALYSIS OF THE PRIMARY EFFICACY ENDPOINT

For Part 2 (Optional Dose Expansion), the primary efficacy endpoint is the change from Baseline to Day 15 in either eye dryness VAS score OR eye discomfort VAS score from the [REDACTED] DED symptom VAS, [REDACTED] based on results from Part 1 (Dose Escalation) Cohorts 1 to 4.

The change in VAS score will be analyzed using a mixed model for repeated measures (MMRM) that includes treatment (INV-102 or vehicle), visit (Days 8 and 15), and treatment-by-visit interaction terms and Baseline as a covariate. The least squares (LS) mean and 95% confidence interval (CI) for each study drug group, the LS mean difference between study drug groups, and the associated p-value and 95% CI for the mean difference will be presented at each visit. Sensitivity analyses may be performed imputing missing data. Full details will be provided in the SAP.

The primary efficacy analyses will be conducted on the mITT and PP populations.

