### Primary endpoint

- Change from Baseline to Day 15 in the Eye Dryness Score from the [REDACTED] DED symptom VAS

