#### **7.1.1. Modified Intention-to-Treat (mITT)**

The mITT population will include all randomized subjects who received at least 1 drop of study drug in the Study Eye and completed at least 1 scheduled post-dosing assessment in the Study Eye. The mITT population will be used to analyze all efficacy endpoints, with subjects included in their randomized study drug regardless of the study drug they actually received.

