#### **7.3.3. Handling of Early Termination Visit Information**

In the event that a subject is terminated early from this study, the early termination data will be assigned to the closest visit. If the closest visit has valid data, the early termination data will be assigned to the next available visit, and treated as observed data for that visit. For subjects who had efficacy measurements taken after the last dose, all observed measurements will be used for analyses.

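### Noncompliance with study drug is listed as a reason to withdraw a subject from the whole study, which can cost true Day 15 outcomes that the mITT analysis could use (small effect, cheap to fix)

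*Protocol*

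**What the plan says.** Protocol Section 8.2 introduces its list with "An investigator may withdraw a subject from the study for the following reasons", and one entry is "Noncompliance with study drug". Section 8.1, on stopping study drug, does not name noncompliance in its visible list, although its investigator-decision and other entries could cover it.

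Protocol Section 7.4 describes a different response: "Noncompliance at Day 8 will result in re-education of the subject", with noncompliance at Day 8 or Day 15 recorded as a protocol deviation. The visible text does not say when re-education gives way to withdrawal. Parts of both 7.4 and 8.2 are redacted.

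On the analysis side:

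- The Part 2 primary endpoint is the "Change from Baseline to Day 15 in the Eye Dryness Score" (SAP Section 4.1).
- The mITT population (Protocol 10.2, SAP 7.1.1) analyses subjects "with subjects included in their randomized study drug regardless of the study drug they actually received". Beyond receiving a drop, it requires only that the subject "completed at least 1 scheduled post-dosing assessment in the Study Eye".
- The primary MMRM includes treatment, "visit (Days 8 and 15), and treatment-by-visit interaction terms and Baseline as a covariate" (Protocol 10.3.2).
- SAP Sections 7.3.2 and 9 rule out imputation of efficacy data.
- SAP Section 7.3.3 assigns early termination data to the closest visit. If that visit already has valid data, "the early termination data will be assigned to the next available visit" and is treated as observed there. The same section uses all efficacy measurements taken after the last dose.
- Compliance below 80% already removes a subject from the PP population (Protocol 10.2, SAP 7.1.2).

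**The concern.** The analysis plan wants outcomes from subjects who stop or skip the drops: mITT is as randomised, and measurements after the last dose count. Section 8.2 lets a site stop collecting those outcomes for exactly these subjects. The primary comparison does not need such withdrawals, because the PP population already deals with compliance.

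Noncompliance is behaviour after randomisation and may depend on treatment, for instance through tolerability or lack of benefit. If subjects leave for that reason, the missing Day 15 values may be informative. The MMRM has no compliance term and handles the gap by assuming data are missing at random given Baseline and Day 8. If that fails, the treatment difference at Day 15 is biased and the mITT result drifts towards a PP result. Because withdrawal is at the investigator's discretion, practice may also vary between sites. In a comparison of about 32 against 16 subjects, each avoidable loss also costs some precision.

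**Working it through.** The plan gives no figure to reproduce. Its sample size is not based on power, and no SD, effect size or dropout rate is stated.

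**Which subjects are exposed.** The visible compliance checks are at Day 8 and Day 15. Noncompliance found at the Day 15 visit need not cost the endpoint, because the VAS is collected at that visit. The exposed group is therefore mainly subjects withdrawn from Day 8 up to Day 15. They remain in mITT with their Day 8 value. Two things can then happen at Day 15:

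- *No exit assessment.* The Day 15 value is missing and the MMRM relies on Baseline and Day 8.
- *Exit assessment after a valid Day 8 value.* An exit on Day 10 is closest to Day 8. That slot is filled, so the value moves to Day 15. An exit on Day 12 is closest to Day 15 and goes there directly. In both cases an earlier value is analysed as Day 15.

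**Bias when the Day 15 value is missing.** Inputs: 32 active and 16 vehicle (Protocol 10.1). Assumed: VAS SD of 25 points, 4 active and no vehicle subjects lost, and lost subjects 10 to 20 points worse at Day 15 than retained ones.

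- Bias in one arm = proportion lost × gap.
- 4/32 = 0.125. 0.125 × 10 = 1.25 points and 0.125 × 20 = 2.5 points, in favour of INV-102.
- SE of the difference with no loss = 25 × √(1/32 + 1/16) = 7.65 points.
- 1.25/7.65 = 0.16 SE and 2.5/7.65 = 0.33 SE.
- With 2 to 6 active subjects lost: 0.0625 × 10 = 0.6 points up to 0.1875 × 20 = 3.75 points.

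These are upper figures for each scenario, because the MMRM recovers whatever part of the gap Baseline and Day 8 explain.

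**The net bias depends on imbalance.** With the same gap in both arms, the bias in the difference is (loss in active − loss in vehicle) × gap. Losing 4 of 32 active and 2 of 16 vehicle is 12.5% in each arm, so the bias is zero. Losing only the 2 vehicle subjects reverses the sign, to 1.25 to 2.5 points against INV-102. In SD units, with a gap of 0.25 to 1.0 SD left after Baseline and Day 8, loss of 10% against 0% gives 0.025 to 0.10 SD, and 20% against 5% gives 0.04 to 0.15 SD.

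**Precision, a separate scenario.** Losing 4 active and 2 vehicle values: SE = 25 × √(1/28 + 1/14) = 8.18, and 8.18/7.65 = 1.069. The increase is about 7% and does not depend on the assumed SD. It too is an upper figure, since it ignores Day 8.

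**The case against.** Withdrawal under Section 8.2 is optional, whereas re-education under 7.4 is stated as what will happen. Redactions after the list in 8.2 and within 7.4 could hold a threshold for withdrawal or a requirement for exit assessments, and SAP 7.3.3 presupposes that early termination data exist. All of this stands, so the point is conditional on that text. Even so, an exit assessment before Day 15 is not a Day 15 outcome.

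A reader might infer that these withdrawals discard the Day 15 outcomes or remove subjects from the primary analysis. The documents do not support that. Day 8 values stay in the MMRM, measurements after the last dose are used, an exit value may fill the Day 15 slot, and noncompliance found at Day 15 need not cost the endpoint. An MMRM also needs no imputation to use incomplete subjects.

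It is also fair to say that missing data are not wholly ignored. Protocol 10.3.2 allows sensitivity analyses with imputation, and SAP 9.2 mentions multiple imputation. But the first is optional. The second is in the section on secondary and other endpoints and points to a Section 7.3.2.3 that the SAP's table of contents does not list.

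Finally, 8.2 covers both parts, and efficacy in Part 1 is only descriptive. The statistical argument is about Part 2, which favours a narrow change to outcome collection over removing the withdrawal reason outright.

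**Conclusion.** The point holds in a limited form. Sections 7.4 and 8.2 describe different responses to noncompliance without saying how they fit together. The response in 8.2 can cost true Day 15 outcomes that the as-randomised mITT analysis could use. The exposure is mainly discretionary withdrawal between Day 8 and Day 15.

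The size is probably small: at most about 1.3 to 2.5 points (0.16 to 0.33 SE) under the one-arm loss assumed above, zero under equal loss and equal gap, and up to about 7% on the SE in the separate equal-rate scenario. The bias and SE figures must not be read as joint effects, because the loss pattern behind the 7% gives no bias when the gap is equal. The SD, loss rates and gap are all assumptions. The p-values are declared descriptive, so what is at stake is how the Part 2 estimate is interpreted, not an error in a stated figure. This is a cheap improvement of low severity, subject to the redacted text.

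**What to change.** Reconcile Protocol Sections 7.4 and 8.2 so that noncompliance with study drug is not by itself a reason to end outcome collection. Add a sentence saying that such subjects, if willing, are asked to attend the already scheduled Day 15 and Day 22 assessments, are analysed in mITT with their observed values, and are excluded only from PP. If the redacted text already says this, a cross-reference between the sections is enough.

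The change concerns data collection only. Decisions on study drug, withdrawals for safety or the subject's best interest, and the subject's own right to leave are untouched. It would leave fewer exit values to be relabelled under SAP 7.3.3 but does not alter that rule.

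The cost is a small protocol edit, since the visits are already scheduled. The downside is some extra site effort with less cooperative subjects, who would stay under the study's eyedrop restrictions through follow-up.
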